4.2 Objectives and Endpoints (Group 2)

OBJECTIVES	ENDPOINTS
Primary Exploratory	
To explore perceptions of the QI strategies from the perspective of primary care clinicians.	No quantitative endpoint. Clinician perceptions will be assessed qualitatively.
Secondary Exploratory	
To explore aspects of effectiveness of the implementation strategies.	For randomized patients, initiation of either a PPI or discontinuation of all antiplatelet therapy based on chart review at week 3.
To explore the feasibility of delivering the patient activation tool	The proportion of patients randomized to receive the activation guide who were sent the guide in the prescribed period of time, as determined by chart review.

OBJECTIVES	ENDPOINTS
To explore the feasibility of delivering the clinician-level QI strategies	Proportion of patients whose clinician was sent the clinician-level strategy by the anticoagulation clinic staff in the prescribed time period per the clinic protocol. We will also separately calculate this endpoint for the two levels of the clinician QI strategy.
To explore process outcomes associated with the clinician notification + nurse facilitation implementation strategy	
For patients randomized to clinician notification + nurse facilitation:
 
Number of days taken for clinicians to send a response message to anticoagulation staff after first receiving the clinician notification.
 
Proportion of clinicians who documented their plan-of-care for the patient in the response message to the anticoagulation staff.
 
Proportion of patients randomized to clinician notification + nurse facilitation for whom the anticoagulation nurse provided patient education.
 
Proportion of patients randomized to clinician notification + nurse facilitation for whom the anticoagulation nurse pended the PPI order.

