To explore process outcomes associated with the clinician notification + nurse facilitation implementation strategy	
For patients randomized to clinician notification + nurse facilitation:
 
Number of days taken for clinicians to send a response message to anticoagulation staff after first receiving the clinician notification.
 
Proportion of clinicians who documented their plan-of-care for the patient in the response message to the anticoagulation staff.
 
Proportion of patients randomized to clinician notification + nurse facilitation for whom the anticoagulation nurse provided patient education.
 
Proportion of patients randomized to clinician notification + nurse facilitation for whom the anticoagulation nurse pended the PPI order.

To explore aspects of effectiveness of the implementation strategies.	
For randomized patients, initiation of either a PPI or discontinuation of all antiplatelet therapy at week 3 as determined by chart review.
 
Documentation of a recommendation by one of the patient's Michigan Medicine clinicians to discontinue antiplatelet therapy or initiate a PPI as indicated by a clinical documentation or by a change in the EHR medication list, ascertained by EHR review.

OBJECTIVES	ENDPOINTS
To explore the appropriateness of antiplatelet therapy used by patients at the time of study randomization.	The clinical appropriateness of antiplatelet therapy at the time of study initiation, classified as either (probably guideline concordant, probably not guideline concordant, or uncertain), based on detailed chart review and in reference to practice recommendations (Appendix 1).
To explore the appropriateness of medication changes in antiplatelet therapy during the trial.	For patients who either stopped antiplatelet therapy or initiated a PPI during the trial, to explore the appropriateness of antiplatelet management according to chart review at week 3. The clinical appropriateness of antiplatelet management will be determined according to pre-specified criteria (probably guideline concordant, probably not concordant, uncertain). See appendix 1 for criteria.

Additional objectives to be explored in qualitative interviews with clinicians:

- Acceptability of the implementation strategy components
- Barriers to successful implementation

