8 END-OF-INTERVENTION/END-OF-STUDY

8.1 Discontinuation of Intervention

8.1.1 Group 1

Use of the implementation strategies will be discontinued for patients who discontinue warfarin therapy or are closed to the anticoagulation clinic service during the first 5 weeks of study participation. Such patients will not be included in the analyses, and will not receive patient assessment #1, #2, or #3.

For patients who discontinue warfarin or are closed to the anticoagulation clinic between week 5 and the end of the study, they will be contacted for patient assessment #1 and #2 but not #3. They will be included in the analysis of the primary and secondary outcomes, as well as the

exploratory outcomes, except those related to patient assessment #3 (e.g., medication adherence, appropriateness of antiplatelet therapy at week 15-17).

8.1.2 Group 2

Use of the implementation strategies will be discontinued for patients who discontinue warfarin therapy or are closed to the anticoagulation clinic service during the first 3-5 weeks of study participation. Such patients will not be included in any analyses.

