8.3 Lost to Follow-Up

8.3.1 Group 1

If a patient is unable to be reached for assessment #1, #2, or #3, the data for the variables associated with that assessment will be coded as missing. If a patient is unable to be reached for assessment #1, no attempt will be made to reach them for assessment #2 or assessment #3. Even if patients are unable to be reached for assessment #1, #2, or #3, chart review will still be performed for that patient to evaluate the exploratory outcomes.

8.3.2 Group 2

Not applicable as no patient assessments will be conducted with group 2 participants. Chart review will be performed for patients in group 2 between study initiation and week 6.

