11.2 General Statistical Approach

11.2.1 Group 1

For the primary and secondary analyses, all participants who undergo randomization will be analyzed. Proportions with confidence intervals will be calculated.

11.2.2 Group 2

For the primary and secondary exploratory analyses, all participants who undergo randomization will be analyzed. Proportions with confidence intervals will be calculated.

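### Group 2: section 8.1.2 drops patients who leave in an open-ended window of 3 to 5 weeks from every analysis, while section 11.2.2 analyses everyone randomized

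*Combined protocol and SAP*

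**What the plan says.** Section 8.1.2 ends use of the strategies for Group 2 patients who stop warfarin or are closed to the service within a window given as a range, and then excludes them: "the first 3-5 weeks of study participation. Such patients will not be included in any analyses". Nothing says whether week 3, 4 or 5 applies to a given patient, or what decides it. The parallel Group 1 rule in section 8.1.1 has one cut-off: "during the first 5 weeks of study participation. Such patients will not be included in the analyses".

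Section 11.2.2 sets the Group 2 analysis set: "For the primary and secondary exploratory analyses, all participants who undergo randomization will be analyzed". Section 4.2 has only those two tiers, so the statement covers every Group 2 endpoint.

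The effectiveness endpoint in section 4.2 is "For randomized patients, initiation of either a PPI or discontinuation of all antiplatelet therapy based on chart review at week 3". A later row repeats it as "initiation of either a PPI or discontinuation of all antiplatelet therapy at week 3 as determined by chart review". The appropriateness endpoint has the same time point: "to explore the appropriateness of antiplatelet management according to chart review at week 3".

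On data collection, section 8.3.2 says: "Chart review will be performed for patients in group 2 between study initiation and week 6". The Group 2 schedule in section 1.4 places delivery of the guide and of the clinician strategy in week 1, and follow-up outreach and facilitation in weeks 2 to 6.

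**The concern.** Two sections define different analysis sets for the same endpoints. Under one, a randomized patient who leaves early counts; under the other, that patient counts nowhere.

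Three features make this more than a wording slip. First, the exclusion is triggered after randomization, and the strategies themselves prompt a review of antithrombotic drugs. The documents do not establish that leaving is unrelated to assignment. Second, with no single end point, whether a patient who leaves in week 4 is in or out can be settled after the chart has been seen, by staff who are not blinded (section 7.3). Third, the window runs past both the week-1 delivery steps and the week-3 reading, so it can remove patients for an event that comes after the thing being measured.

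At stake are the by-arm descriptive proportions meant to inform the later clinic-wide trial, above all whether the guide and the clinician message were sent on time.

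**Working it through.** The plan states no Group 2 sample-size or precision figure (section 11.1.2 is marked not applicable), so there is none to reproduce. The check compares the texts and adds a small sensitivity calculation.

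**Which endpoints the exclusion reaches**

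| Group 2 endpoint (section 4.2) | When it is determined | Effect of an exit in weeks 3 to 5 |
|---|---|---|
| Guide sent; clinician message sent | Week 1 (section 1.4) | Already settled; cannot change |
| Medication change; appropriateness | Week 3, by chart review | Week-3 status has occurred and falls inside the chart-review period to week 6 |
| Clinician response, nurse education, pended order | Depend on steps that can run over weeks 2 to 6 | May be cut short, because section 8.1.2 discontinues the strategy |
| Clinician perceptions (primary exploratory) | Clinician interview | Not removed by dropping a patient's chart data |

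The first two rows lose usable information under section 8.1.2. The third needs its own handling. The fourth is unaffected.

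**How far a removal can move a proportion**

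Inputs: N = 8 to 16 patients (section 6.1.2). The documents give no exit rate, so k = 0, 1 or 2 removals is an assumption. An all-randomized week-3 proportion of 50% is also an assumption.

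One patient is 1/16 = 6.25% to 1/8 = 12.5% of the sample. With x patients changed among N, the proportion after k removals is x/(N − k) if those removed had no change, and (x − k)/(N − k) if they all had one. The normal-approximation 95% half-width at p = 0.5 is 1.96 × √(0.25/(N − k)).

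| N | k | Removed had no change | Removed had a change | Half-width |
|---|---|---|---|---|
| 8 | 0 | 4/8 = 50% | 4/8 = 50% | 0.346 |
| 8 | 1 | 4/7 = 57% | 3/7 = 43% | 0.370 |
| 8 | 2 | 4/6 = 67% | 2/6 = 33% | 0.400 |
| 16 | 0 | 8/16 = 50% | 8/16 = 50% | 0.245 |
| 16 | 1 | 8/15 = 53% | 7/15 = 47% | 0.253 |
| 16 | 2 | 8/14 = 57% | 6/14 = 43% | 0.262 |

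One removal shifts the proportion by about 7 points at N = 8 and 3 points at N = 16; two shift it by about 17 and 7 points. All these shifts lie well inside the half-width. Section 1.4 expects one or two patients per clinician, so a single removal can also empty a cluster for the chart-review endpoints.

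**The case against.** Little depends on these numbers. All Group 2 endpoints are exploratory, section 11.4.2 states no hypothesis, and the primary exploratory endpoint is qualitative and comes from clinicians. Entry requires anticipated warfarin use of at least 90 days, and eligibility is confirmed again at entry, so there may be no exits at all among 8 to 16 patients. This stands, and it limits the weight of the point.

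Section 8.1.2 could also be read as a specific exception to a general statement in section 11.2.2, since a patient off warfarin is no longer on the combination therapy that the strategies target. That is a possible intention, but neither section says so. As an exception it would still have no defined end and would still discard delivery data already settled in week 1.

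Three stronger readings are tempting, and the documents do not support them:

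- **That recorded week-3 outcomes are deleted.** Chart review runs to week 6, and no text says that week-3 status is abstracted before a later exit. What holds is that the status has occurred and can still be read from the chart.
- **That every randomized patient should stay in every process endpoint.** Section 8.1.2 discontinues the strategies for these patients. Counting them without a further rule would score as failures steps that were stopped as planned.
- **That 6% to 12.5% measures the bias.** It is one patient's share of the sample, not an effect on any result.

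**Conclusion.** The contradiction holds: sections 8.1.2 and 11.2.2 cannot both define the Group 2 analysis set, and the exclusion window has no single end point. The exclusion depends on a post-randomization event, can drop patients whose week-3 status remains readable, and discards week-1 delivery data for no stated reason.

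The consequence is minor. It reaches only exploratory descriptive proportions, and no planned Group 2 test or decision rule turns on it. The shifts shown rest on the assumed removals and the assumed 50%; with no exits the effect is nil. A reader might infer that the rule biases the comparison of arms. The documents neither show that exits differ by arm nor rule it out.

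Section 8.1.1 conflicts with section 11.2.1 in the same way for Group 1. That is a separate matter and is not assessed here.

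**What to change.** Remove the sentence in section 8.1.2 that excludes these patients from analysis, and let section 11.2.2 govern. Then state, in section 11.2.2 or 11.7.2:

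- Every randomized Group 2 patient stays in the week-1 delivery endpoints (guide sent, clinician message sent).
- Patients who leave after week 3 stay in the week-3 medication-change and appropriateness endpoints.
- Patients who leave before week 3 are shown as a separate category by arm. So are process steps not done because the strategy was discontinued (clinician response, nurse education, pended order). Neither is counted as a failure or deleted.

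The range in section 8.1.2 also serves as the rule for stopping the strategies. In that role the sponsor must reconcile it separately; this point takes no position on it.

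The cost is one deleted sentence, a matching line in section 11, and one more reporting category. No new data collection is needed, because chart review to week 6 is already planned.

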8.2 Participant Discontinuation/Withdrawal from the Study

8.2.1 Group 1

Patients or clinicians who wish to discontinue any study interview will have the interview discontinued.

8.2.2 Group 2

Clinicians who wish to discontinue any study interview will have the interview discontinued. No patient outreach or assessments will be conducted with group 2 participants.

8.3 Lost to Follow-Up

8.3.1 Group 1

If a patient is unable to be reached for assessment #1, #2, or #3, the data for the variables associated with that assessment will be coded as missing. If a patient is unable to be reached for assessment #1, no attempt will be made to reach them for assessment #2 or assessment #3. Even if patients are unable to be reached for assessment #1, #2, or #3, chart review will still be performed for that patient to evaluate the exploratory outcomes.

8.3.2 Group 2

Not applicable as no patient assessments will be conducted with group 2 participants. Chart review will be performed for patients in group 2 between study initiation and week 6.

9 STUDY ASSESSMENTS AND PROCEDURES

9.1 Eligibility Assessment

9.1.1 Group 1

Before identifying eligible patients, the 12 participating clinicians will be selected at random. Next, the patients who fall into each clinician cluster, and who meet eligibility criteria, will be identified. These two tasks will be accomplished using a MiChart workbench report (previously developed by the anticoagulation clinic) that contains data on relevant eligibility criteria. All eligible patients and clinicians will be identified prior to commencement of the interventions.

Each week, 8-10 patients from the list of eligible patients will enter into the study, after confirming that they still meet eligibility criteria. These patients will be added to a separate MiChart report for the participating anticoagulation clinic nurses, identifying the patients and the QI implementation strategies to which they have been randomized.

9.1.2 Group 2

A convenience sample of 8 primary care clinicians who meet eligibility criteria for group 2 will be selected. Next, the patients who fall into each clinician cluster, and who meet eligibility criteria, will be identified. These two tasks will be accomplished using a MiChart workbench report (previously developed by the anticoagulation clinic) that contains data on relevant eligibility criteria. All eligible patients and clinicians will be identified prior to commencement of the interventions.

Each week, up to 12 patients from the list of eligible patients will enter into the study, after confirming that they still meet eligibility criteria. These patients will be added to a separate MiChart report for the participating anticoagulation clinic nurses, identifying the patients and the QI implementation strategies to which they have been randomized.

9.2 Qualitative Assessments with Participants in Group 1

Qualitative assessments will be conducted with clinicians, patients, and anticoagulation clinic staff to elicit feedback on the appropriateness and feasibility of the implementation strategies. Semi-structured interview guides have been developed to guide each assessment. These interview guides will be iteratively revised throughout the study to allow initial assessments to inform later assessments and ensure capture of all relevant information.

9.2.1 Clinicians:

One-time semi-structured qualitative interviews will be conducted with up to 12 clinicians who received communications from the anticoagulation clinic as part of this project. The interviews will be conducted 5-10 weeks after the last patient in the clinician-cluster entered into the study. Clinicians will be sent an invite to participate in an hour-long phone or zoom interview at their institutional email address by a research assistant. Clinicians will be offered a \$100 gift card as an incentive for participation. Qualitative interviews with clinicians will focus on clinicians'

perceptions of the acceptability of the QI strategies and on feasibility of responding to the messages and initiating medication changes for GI bleeding risk reduction. Written informed consent will be obtained using SignNow software.

9.2.2 Patients:

- **Patient Assessment #1 (Week 5):** A research assistant will contact all patient participants by phone at week 5 to administer patient assessment #1, expected to take no more than 10 minutes to complete, with the patient's permission. This questionnaire will ask patients about the medications they used ~30 days prior and the medications that they currently use. All patients will be asked whether they have had any changes in their medications in the past month, or if they have had a discussion with a healthcare provider about any medication changes or their risk of bleeding. Patients who were randomized to receive the activation tool will additionally be asked whether they recall receiving any educational materials about bleeding risk from the anticoagulation clinic to assess the feasibility of delivering patient education and activation materials. If the patient self-reports any use or non-use of medications that contradicts the information in their MiChart medication list, the research assistant will send a MiChart message to the patient's anticoagulation clinic nurse so that the nurse can reconcile the chart. No remuneration will be offered with this patient contact. We request a waiver of informed consent for patient contact #1. **Data on the ability to reach patients for this evaluation will be used to assess the pilot trial's primary outcome. Up to three contact attempts over a period of 2 weeks will be made to reach each patient for assessment #1.**
 - At the end of this call, patients who self-report having had a discussion with their clinician and those who were randomized to receive the patient activation tool will be invited to take part in a second 60-minute phone research interview within the next 3 weeks(patient assessment #2). All patients who complete assessment #1 will additionally be invited to participate in another medication review call at week 15-17 to assess durability of medication changes (patient assessment #3).
- **Patient Assessment #2 (Week 5-8):** A research assistant will contact a subset of participants (as described above) to participate in an hour-long semi-structured qualitative phone or zoom interview for patient assessment #2. The interview will elicit patient perceptions about the patient activation tool and about any discussions the patient may have had with one of their clinicians about their risk of bleeding and/or ways to reduce that risk. Prior to the interview, patient's will be provided with an informed consent document approved by the IRB at the University of Michigan and given the chance to ask any questions they may have. Patient's will then be asked to provide verbal consent before the interview may begin. Patient's will be advised that participation is entirely voluntary and choosing not to participate will not affect the care they may receive at Michigan Medicine. They will also be instructed that they can decline to answer any questions or end the interview at any time shall they wish. As all interviews will be conducted over the phone or zoom, and do not deal with sensitive or stigmatized subjects, we request a waiver of documentation of written informed consent for patient

assessment #2. Patients will receive a \$20 gift card as remuneration for participating in this assessment. Patient remuneration will be sent through the University of Michigan treasurer's office human subjections incentives payment program gift card payment option.

- **Patient Assessment #3 (Week 15-17):** A brief 15-20 minute medication phone interview that asks patients about their use of antiplatelet drugs and PPIs at the time of the call, instructions they received from their clinician on how to use any of these medications, and about adherence to any antiplatelet drugs or PPIs the patient self-reports using. If the patient self-reports any use or non-use of medications that contradicts the information in their MiChart medication list, the research assistant will send a MiChart message to the patient's anticoagulation clinic nurse so that the nurse can reconcile the chart. Prior to the interview, patient's will be provided with an informed consent document approved by the IRB at the University of Michigan and given the chance to ask any questions they may have. Patient's will then be asked to provide verbal consent before the interview may begin. Patient's will be advised that participation is entirely voluntary and choosing not to participate will not affect the care they may receive at Michigan Medicine. They will also be instructed that they can decline to answer any questions or end the interview at any time shall they wish. As all interviews will be conducted over the phone, do not deal with sensitive or stigmatized subjects, we request a waiver of documentation of written informed consent for patient assessment #3. Patients will receive a \$10 gift card as remuneration for participating in this assessment. Patient remuneration will be sent through the University of Michigan treasurer's office human subjections incentives payment program gift card payment option.

9.2.3 Anticoagulation clinic staff:

One-time semi-structured qualitative interviews will be conducted with all anticoagulation clinic staff members who participated in the pilot project. Anticoagulation clinic staff members will be sent an invite to participate in an hour-long phone or zoom interview at their institutional email address by a research assistant at the conclusion of the pilot study. Interviews with staff will be conducted during normal work hours and anticoagulation clinic staff will not receive additional remuneration above their regular pay for participating in the research interview. Qualitative interviews with anticoagulation clinic staff will focus on eliciting staff members' perceptions of the acceptability of the implementation strategies and on feasibility of delivering the implementation strategies to both patients and clinicians. Written informed consent will be obtained using SignNow software.

9.3 Qualitative Assessments with Participants in Group 2

Qualitative assessments will be conducted with clinicians to elicit feedback on their perceptions of the implementation strategies. A semi-structured interview guide has been developed to guide the assessment. The interview guide will be iteratively revised throughout the study to

allow initial assessments to inform later assessments and ensure capture of all relevant information.

9.3.1 Clinicians:

One-time semi-structured qualitative interviews will be conducted with up to 8 primary care clinicians who received communications from the anticoagulation clinic as part of this project. The interviews will be conducted 3-6 weeks after the last patient in the clinician-cluster entered into the study. Clinicians will be sent an invite to participate in an hour-long phone or zoom interview at their institutional email address by a research assistant. Clinicians will be offered a \$100 gift card as an incentive for participation. Qualitative interviews with clinicians will focus on clinicians' perceptions of the acceptability of the QI strategies and on feasibility of responding to the messages and initiating medication changes for GI bleeding risk reduction. Written informed consent will be obtained using SignNow software.

